### **LOST TO FOLLOW-UP**

A participant will be considered lost to follow-up if he or she fails to complete the post intervention forms and study staff are unable to contact the participant after 5 attempts.

The following actions must be taken if a participant fails to return post-intervention forms or equipment:

- Before a participant is deemed lost to follow-up, the investigator or designee will make every effort to regain contact with the participant (where possible, up to 5 telephone calls and/or emails, and if necessary, a mailed letter to the participant's last known mailing address or local equivalent methods. These contact attempts will be documented in the participant's study file.
- Should the participant continue to be unreachable, she will be considered to have withdrawn from the study with a primary reason of lost to follow-up.

## **15.0 Risks to Subjects\***

We anticipate minimal risk to participants for participating in the study.

### **Known Potential Risks**

Primary risks of the study include: a) embarrassment or discomfort with study questions; b) emotional, social, or physical harms resulting from the suggested behavioral modifications; c) inadvertent disclosure of data; d) Inadequacy of informed consent; or e) other risks that are unlikely to occur, but could. We discuss below methods to protect against these risks:

Embarrassment or discomfort with detailed behavioral questions or institutional structure can occur. This risk is minimized by ensuring that participants know they do not have to participate or may only answer the questions that they feel comfortable answering. We will refer patients to seek care from their regular medical doctor in the event the participant experiences any emotional or physical discomfort or will remind them that they can stop participation in the study at any point in time.

#### **Data security:**

- Data will be encrypted at all times, from the point of entry into RedCAP to the point of backup and to analysis. Data will be encrypted using standardized software (e.g., 128-bit, PGP).

## PROTOCOL TITLE: Testing mHealth Delivery of Cognitive Behavioral Therapy for Insomnia to Breast Cancer Survivors

- Data entered into RedCAP will be de-identified at all times. RedCAP results will be linked to a Survey ID number rather than names to minimize risk of inadvertent disclosure.
- Transfer of data will be overseen by [name] and conducted using password protected and encrypted files.
- Data will not be released to non-study staff at any time.
- Any audio-recorded data will be transcribed without identifiers and audio recordings will be destroyed after quality control or within five years.

## 16.0 Potential Benefits to Subjects\*

### Known Potential Benefits

The potential benefits from participation in this study include improvement in insomnia symptoms among randomized controlled trial intervention participants and in the longer term, dissemination of cognitive behavioral therapy for insomnia for breast cancer survivors. Knowledge gained from this project will be used to inform design of a commercial product to treat insomnia among cancer survivors. In view of the potential information to be gained, and how it will ultimately be able to contribute to new approaches to providing care to this survivor population, the minimal risks do not outweigh the potential for benefit.

## 17.0 Data Management\* and Confidentiality

### ○ STATISTICAL HYPOTHESES

- Primary Endpoint(s): Insomnia Severity Index

We hypothesize that, compared to participants who receive a control intervention, participants who receive Cognitive Behavioral Therapy for Insomnia via the Sleep Helper skill will have lower ISI scores at the end of the six-week intervention. Alternatively, our null hypothesis is that there will be no difference in the ISI score between groups at the end of the six-week intervention. Thus our primary efficacy outcome is based on the continuous ISI scale. We plan to also conduct a categorical analysis: we further hypothesize that a greater percentage of those in the intervention arm will have a clinically significant reduction in ISI score to <14, or sub-threshold insomnia, than in the control arm.

- Secondary Endpoint(s): CSD Metrics

Our statistical objective is exploratory in that we are interested in whether we are seeing changes in metrics of the CSD. We will evaluate the following CSD metrics: sleep efficiency, wake after sleep onset, sleep onset latency, total sleep time and sleep quality.

- Exploratory Endpoint(s): We will analyze whether we see differences in ISI change by level of engagement and satisfaction with the intervention.

### ○ SAMPLE SIZE DETERMINATION

## PROTOCOL TITLE: Testing mHealth Delivery of Cognitive Behavioral Therapy for Insomnia to Breast Cancer Survivors

We based our power calculations on the null hypothesis of no significant mean adjusted difference between groups post-intervention on a continuous total ISI score, after controlling for baseline score using Analysis of Covariance (ANCOVA). A systematic review and meta-analysis published in 2016 showed a large effect size of  $d=0.77$  (95% CI 0.60-0.93) at post-treatment across seven randomized controlled trials {Johnson, 2016 #740}. A recent study of internet-based CBT-I among breast cancer survivors found an effect size of 1.17 where the outcome was the ISI {Zachariae, 2018 #69}.

We used Proc GLMPOWER in SAS Version 9.4 to calculate a series of required sample sizes with covariate-outcome correlations (0.5-0.8) with a desired power of 80% to detect effect sizes between .50 and .80 (medium to large). N values included in the table are for total sample size. Alpha was set at .05 (2-sided test).

Effect size	Correlation 0.5	Correlation 0.6	Correlation 0.7
0.5	N=98	N=84	N=68
0.65	N=58	N=50	N=40
0.8	N=40	N=34	N=28

Estimating a conservative effect size (based on prior literature) of 0.65 and a pre-post correlation of 0.5, we would need N=58 participants, or n=29 per arm. We will aim to recruit N=76 total (n=38 per arm) to allow for drop out of up to 30%.

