**12.0 Local Number of Subjects**

12.1 We plan to enroll up to 76 patients in the study total, with about one third accrued locally.

We anticipate screening approximately 150 women in order to identify n=76 for the RCT.

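### Recruiting 76 covers dropout of about 23%, not the stated 30%: at 30% loss about 53 participants remain against the 58 required, and power is about 76%

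*Combined protocol and SAP*

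**What the plan says.** The Sample Size Determination part of section 17.0 bases the calculation on the post-intervention ISI total score, "after controlling for baseline score using Analysis of Covariance (ANCOVA"). The table was built "with a desired power of 80% to detect effect sizes between .50 and .80 (medium to large"), and "Alpha was set at .05 (2-sided test"). The row and column used are given as "Estimating a conservative effect size (based on prior literature) of 0.65 and a pre-post correlation of 0.5", from which "we would need N=58 participants, or n=29 per arm". The next sentence sets the recruitment target: "We will aim to recruit N=76 total (n=38 per arm) to allow for drop out of up to 30" percent.

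Section 12.0 (Local Number of Subjects) repeats the total as a ceiling: "We plan to enroll up to 76 patients in the study total". Section 14.0 allows replacement only of people who are randomized and never receive the intervention; those who receive it and later leave are not replaced.

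**The concern.** The 30% allowance is there to leave the required 58 participants after losses. The number left after 30% loss is 70% of those recruited, so the target should be 58 divided by 0.70. Adding 30% to 58 gives a smaller number, and 76 looks like the result of that addition. If so, the protocol claims a robustness to dropout that the design does not have.

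The point has practical weight because the protocol treats dropout of this order as plausible. Its background (3.3) cites 20–30% in brief CBT-I trials, and section 3.0 cites up to 40% for web-based therapy. If loss comes in between about 24% and 30%, the primary comparison would fall below its target power while the protocol says that it would not. A non-significant result could then be credited with more power than the trial had.

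**Working it through.** **Inputs** (Sample Size Determination, section 17.0, except where noted)
- Standardized effect size d = 0.65
- Pre-post correlation r = 0.5
- Two-sided alpha 0.05, desired power 80%
- 1:1 allocation (section 6.0, Randomization)
- Required 58, recruited 76, dropout up to 30%

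**Step 1. Reproduce the plan's 58.** For a two-arm ANCOVA with one baseline covariate:
- residual SD = √(1 − r²) = √0.75 = 0.866
- noncentrality = (d / residual SD) / √(1/n₁ + 1/n₂)
- degrees of freedom = N − 3, with power from the noncentral t distribution

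At N = 58 (29 + 29): 0.65 / 0.866 = 0.7506; √(2/29) = 0.2626; noncentrality = 2.858; df = 55; critical t = 2.004; power = 80.2%. At N = 56 power is 78.7%, so 58 is the smallest even total that reaches 80%. The same method reproduces all nine cells of the plan's table (98/84/68, 58/50/40, 40/34/28). The base calculation is therefore sound, and the model used here matches the plan's.

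**Step 2. How 58 became 76.**
- 58 × 1.30 = 75.4, rounded up to 76; per arm, 29 × 1.30 = 37.7, rounded up to 38. This matches the plan.
- 58 / (1 − 0.30) = 82.9, rounded up to 83; with equal arms 29 / 0.70 = 41.4, so 42 per arm and 84 in total. This does not match the plan.

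**Step 3. What 30% loss leaves.** 76 × 0.70 = 53.2, about five short of 58.

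**Step 4. Power by number evaluable** (d = 0.65, r = 0.5):

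| Evaluable N | Loss from 76 | Power |
|---|---|---|
| 76 | 0% | 89.8% |
| 68 | about 10% | 86.2% |
| 61 | about 20% | 82.2% |
| 58 | 23.7% | 80.2% |
| 54 | 28.9% | 77.2% |
| 53 | 30.3% | 76.4% |
| 52 | 31.6% | 75.6% |

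**Step 5. Dropout that 76 does cover.** 1 − 58/76 = 18/76 = 23.7%.

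**Step 6. Sensitivity at N = 53.**
- With r = 0.6 and d = 0.65, power is 82.6%.
- With d = 0.77 (the meta-analytic estimate the plan cites) and r = 0.5, power is 88.7%.
- With d = 0.60 (the lower confidence limit of that estimate) and r = 0.5, power is about 70%.
- Power returns to 80% at d of about 0.68 (r = 0.5) or r of about 0.56 (d = 0.65).

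**The case against.** The arithmetic is hard to dispute, so the best counter-case is about size and likelihood.

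- **The gap is small.** Power falls by less than four points, and only at the far end of the range. Up to 23.7% loss the trial meets its target, and at 20% loss power is 82.2%. The estimand, the test and the type I error are untouched. This stands, and it is why a wording change is enough.
- **The planning values are cautious.** The plan chose an effect below both estimates that it cites (0.77 and 1.17) and the lowest correlation in its table. Slightly better values restore 80% at 53. That is true, but the 30% claim is attached to 0.65 and 0.5, and the cited interval also contains 0.60, where power at 53 is about 70%.
- **The plan never states a power at 30% dropout.** The 80% is the desired power at 58. That is literally correct. Still, an allowance for dropout has no purpose other than to protect the requirement stated in the sentence before it.
- **Missing outcomes may be fewer than dropouts.** People who stop using the program are still asked for the final forms (14.0), the gift card and device depend on completing them (13.0), and there are repeated contact attempts (14.0). These measures may well lower the loss rate. They do not change what 30% loss would leave.
- **Multiple imputation is planned when loss exceeds 10%.** Its main role is to reduce bias. With mainly baseline predictors it would generally be expected to restore little information about a missing final ISI; this is a general expectation and was not computed here. The plan does not count imputation as a source of power.
- **Readers would see the achieved numbers.** CONSORT reporting and a confidence interval would show the actual precision, so the risk of misreading a null result is limited. It does not make the sentence correct.

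**Conclusion.** The concern holds. A target of 76 leaves the required 58 only if loss is at most 23.7%. At the stated 30% it leaves about 53, and power for the primary ISI comparison is about 76% rather than the 80% target. This rests on the plan's own effect size, correlation, alpha and ANCOVA model, with loss shared about equally between arms and power carried by observed outcomes. Nothing elsewhere in the protocol closes the gap: enrolment is capped at 76, and withdrawals after receipt of the intervention are not replaced. The consequence is modest, but the sentence is wrong as written, and it is the stated reason for recruiting 76 rather than 58.

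**What to change.** Keep 76 and correct the dropout sentence in section 17.0, for example: *With N=76 (38 per arm), 80% power (effect size 0.65, correlation 0.5) is retained for dropout of up to 23%. At 30% dropout, about 53 participants would be evaluable and power would be about 76%.* This costs one sentence and no additional participants; the stated tolerance simply becomes less favourable.

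If the sponsor prefers to keep the claim of 80% power at 30% loss, the target becomes 84 (42 per arm), since 84 × 0.70 = 58.8. That means eight more participants and matching changes wherever 76 appears: the study summary (1.0), the specific aim (2.0), section 12.0 and section 17.0.

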### ○ POPULATIONS FOR ANALYSES

For our primary and secondary analyses we will be using intent to treat. In tertiary analyses we will conduct analyses by adherence (median frequency of engagement).

### ○ STATISTICAL ANALYSES

#### General Approach

**Aim 3.** In the clinical trial analysis we will follow CONSORT guidelines to descriptively present means and frequencies of baseline characteristics in Table 1, and will follow guidelines in all analyses and reporting. We will consider  $p<0.05$  as the level of significance and will use 2-tailed tests.

#### Analysis of the Primary Endpoint(s)

The ISI is a seven-item questionnaire with response categories from 0-4 (total score 0-28) asking about sleep patterns and specifically characterizing insomnia over the two weeks prior. Our primary analysis endpoint will use this continuous ISI score.

We will test for assumptions of linearity of regression, homogeneity of error variances, independence of error terms, normality of error terms, and homogeneity of regression slopes. We will use analyses of covariance (ANCOVA) to compare the two groups, which controls for baseline ISI values. We will analyze the treatment effect using the intent-to-treat principle. Descriptive statistics will examine differences in baseline variables between completers and dropouts. If important differences are observed (suggesting the data are missing under a “Not Missing at Random” mechanism) or the loss to follow-up rate exceeds 10%, the primary analysis will be tested through multiple imputation of the ANCOVA model, where potential predictors of dropout will be included in the imputation model, e.g., response to a baseline question asking about the degree of motivation of the participants to stay in the study.

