### 6.0 Procedures Involved\*

**Type of study design.** We will conduct a six-week, individual randomized controlled trial with two arms. While recruitment is being conducted at various locations, the intervention is delivered remotely and all data collection and analyses will be conducted through Medstar Health Research Institute.

Individuals who express an interest in the study will be screened for eligibility by phone. Questionnaires will be completed in REDCap. Study staff will download screening results and calculate ISI scores. Participants will be notified of eligibility by phone or email within 3 business days of completing the eligibility screening.

If the participant is eligible and wishes to proceed with study enrollment, she will receive a personalized REDCap link by email with baseline forms. Study staff will be available to administer the forms by phone or to send hard copies by mail if the individual prefers. Prior to randomization we will collect information on basic demographics (e.g. age, body mass index, education, income, marital status), medical history (e.g. comorbidities, time since treatment, concurrent medication), and lifestyle habits (e.g. physical activity, smoking, alcohol consumption, diet) as well as our primary outcome of the Insomnia Severity Index (ISI). The ISI defines 'no clinically significant' insomnia as a score of 0-7, 'sub-threshold' insomnia as a score of 8-14, 'moderate severity clinical' insomnia a scores of 15-21, and 'severe clinical' insomnia as a score of 22-28.

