#### ***Consent Procedures and Documentation***

Informed consent will be conducted by phone. Anyone called will first be read the consent for screening form, which requires only a verbal consent so as to minimize the potential to link PHI. Individuals will be asked a series of questions by a MHRI research assistant or clinical research coordinator to determine eligibility (including the Insomnia Severity Index), and will be notified of whether they are eligible within 3 business days.

If deemed eligible, participants will receive a copy of the full consent form by email. The CRC will then set up a phone call where study staff will review the full consent form and ask individuals if they have any questions or concerns. Once informed consent has been completed, participants will receive a subject ID, which will be linked to a personalized survey administered via REDCap. Participants will also be able to view a written version of the informed consent on a landing page in REDCap, which they must agree to before continuing to complete baseline forms. The landing page will include a single page summary of the research, with an option to download the full informed consent again (although they will have previously received the full form by email). Both the text that will be on the landing page and the full informed consent are included in this application.

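### Two ISI scores appear to be collected before randomisation, but the primary ANCOVA and its power calculation use one; adding the screening score could modestly improve precision

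*Combined protocol and SAP*

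**What the plan says.** Section 22.0 (Consent Procedures and Documentation) has staff ask screening questions by phone "to determine eligibility (including the Insomnia Severity Index"). Section 6.0 adds that staff score the ISI from the screening results, and inclusion criterion 6 in Section 10.0 requires a score of at least 8.

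Section 6.0 then describes a personalised REDCap link to baseline forms for women found eligible. It lists what is gathered before randomisation: demographics, history and habits, "as well as our primary outcome of the Insomnia Severity Index (ISI"). The Data collection paragraph of the same section repeats the ISI among the REDCap baseline data.

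The sample size (Section 17.0, Sample Size Determination) tests the post-intervention difference "after controlling for baseline score using Analysis of Covariance (ANCOVA"), and its planning values are given as "Estimating a conservative effect size (based on prior literature) of 0.65 and a pre-post correlation of 0.5". The primary analysis in Section 17.0 reads "We will use analyses of covariance (ANCOVA) to compare the two groups, which controls for baseline ISI values". No section says which measurement is the baseline value, and none plans to use a second one.

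**The concern.** If every randomised woman has two pre-randomisation ISI scores, a model with only one leaves a prognostic measurement unused. Two noisy readings of the same construct usually explain more of the outcome variance than one, which narrows the primary confidence interval. That is worth having in a trial of 76, where loss at the planned ceiling of 30% leaves about 53 completers against the 58 the calculation calls for.

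A smaller matter goes with it. Because the covariate is not defined, the text could be met by the screening score, the baseline-form score or both. Each is valid under randomisation, but they give different estimates and p-values. The logistic model for the categorical analysis also relies on an undefined baseline ISI.

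**Working it through.** **Inputs from the documents.** "Alpha was set at .05 (2-sided test"); calculations run "with a desired power of 80% to detect effect sizes between .50 and .80 (medium to large"); effect size d = 0.65; one covariate with correlation r = 0.5; 1:1 allocation; 76 recruited, up to 30% dropout.

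**Inputs not in the documents.** The correlation r12 between the two pre-scores, and the screening score's own correlation with the outcome. Both are varied below.

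**Step 1: reproduce the plan's figure.** With one covariate, R² = 0.5² = 0.25. The noncentrality is d/√(1 − R²) × √N/2, with N − 3 degrees of freedom. At N = 58: 0.65/0.8660 × 3.808 = 2.858 on 55 df, power 80.2%. This matches "a pre-post correlation of 0.5, we would need N=58 participants, or n=29 per arm". The same function reproduces all nine cells of the plan's table, so the plan is indeed powered on a single pre-score.

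**Step 2: planned dropout.** 76 × 0.7 = 53.2, so about 53 completers. Noncentrality is 0.7506 × 3.640 = 2.732 on 50 df, power 76.4%.

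**Step 3: both scores, equally predictive.** If each correlates 0.5 with the outcome, R² = 2(0.5²)/(1 + r12), with one further degree of freedom lost.

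| r12 | R² | Power, 53 completers | Power, 58 evaluable | N for 80% |
|---|---|---|---|---|
| one score only | 0.250 | 76.4% | 80.2% | 58 |
| 0.6 | 0.3125 | 79.9% | 83.4% | 54 |
| 0.7 | 0.294 | 78.8% | 82.5% | 56 |
| 0.8 | 0.278 | 77.9% | 81.6% | 56 |
| 0.9 | 0.263 | 77.1% | 80.8% | 58 |

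Residual variance falls from 0.75 to between 0.6875 (r12 = 0.6) and 0.737 (r12 = 0.9), that is by 8% to 2%. The confidence interval narrows by the square root of that ratio, about 4% to 1%.

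**Step 4: screening score less predictive.** With correlations r1 (baseline form) and r2 (screening), R² = (r1² + r2² − 2·r1·r2·r12)/(1 − r12²). For r1 = 0.5, r2 = 0.40, r12 = 0.8: (0.25 + 0.16 − 0.32)/0.36 = 0.25. For r2 = 0.45, r12 = 0.9: (0.25 + 0.2025 − 0.405)/0.19 = 0.25. In both cases the second score adds nothing, and power at 53 completers goes from 76.40% to 76.37%. That 0.03-point loss is the cost of the extra degree of freedom.

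**Step 5: what would reach 80% at 53 completers.** R² of about 0.315 is needed, which under Step 3 means r12 of about 0.59 or lower (0.5/0.315 − 1).

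**The case against.** The strongest reply is that nothing is wrong. ANCOVA on one baseline score gives a valid treatment effect, and the sample size reproduces exactly. This stands: the point is an efficiency suggestion.

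Two administrations are inferred. No section says that the ISI is repeated, or rules out carrying the screening value forward. This also stands, although separate screening and baseline steps make two the natural reading.

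The gain may be small. The screening score is truncated at 8 or more and lies further from the outcome. Its two-week recall may overlap with that of the baseline form, and it is taken by phone whereas the forms go by default through a link. Each could weaken what it adds, so the honest range starts at zero.

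Three stronger readings are tempting, and the documents do not support them:

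- A reader might infer that the second score restores the planned power. At 53 completers every value in the table is below 80%. The gap comes from the dropout allowance: 58 × 1.3 = 75.4 gives the planned 76, whereas 58/0.7 = 82.9 calls for 83. That is a separate issue, and a covariate does not reliably close it.
- A reader might infer that the change is free. It needs no new assessment, but Section 22.0 takes screening data under verbal consent and issues a subject ID only after full consent. Linkage and permitted use therefore have to be confirmed. Section 6.0 mentions a protected recruitment document in which study IDs are assigned, which suggests that linkage is feasible but does not settle permission.
- A reader might infer that the primary model has been left open to choice. Section 6.0 speaks of screening results on the one hand and baseline data on the other, so baseline ISI most naturally means the form score. One clarifying line is enough.

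**Conclusion.** The plan appears to collect two pre-randomisation ISI scores and uses one. Its analysis is valid; using both is a modest, optional improvement. With both scores correlated 0.5 with the outcome and 0.6 to 0.9 with each other, the gain at d = 0.65 is 0.7 to 3.5 power points with 53 completers (76.4% to 77.1–79.9%) and 0.6 to 3.2 points with 58 (80.2% to 80.8–83.4%). It is zero if the screening score tells nothing beyond the baseline-form score, and the loss in that case is about 0.03 points. The size rests on two correlations that the documents do not give, and on the reading that the ISI is administered twice.

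**What to change.** Before outcomes are examined by arm, amend Section 17.0 (Analysis of the Primary Endpoint(s)) as follows:

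1. Define baseline ISI as the score from the REDCap baseline forms. This also settles the covariate in the logistic model.
2. Prespecify one primary ANCOVA: post-intervention ISI on arm, baseline-form ISI and screening ISI. Enter the two scores as separate covariates, and do not leave their mean as an alternative, since that would reopen the choice of model.
3. Keep the ANCOVA with baseline-form ISI alone as a sensitivity analysis.
4. If the multiple imputation is triggered, include both scores in the imputation model so that it matches the analysis.

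First confirm that screening scores can be linked to the subject ID and used under the consents given. If they cannot, use the baseline-form ISI alone; item 1 is still worth making. The cost is a few sentences in the analysis plan, one degree of freedom and the linkage check. The dropout allowance needs its own correction.
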